## Document History

Document	Version Date
Ammendment 1	18 August 2022
Original protocol	29 June 2022

This amendment incorporates all revisions to date, including amendments made at the request of country health authorities and IRBs/ECs and any global protocol administrative change letter(s).

## Protocol Amendment Summary of Changes Table

### Amendment 1 (18 August 2022)

**Overall Rationale for the Amendment:** This study is being amended to CCI

Section # and Name	Description of Change	Brief Rationale	Substantial or Nonsubstantial
• [REDACTED]	CCI [REDACTED]	[REDACTED]	[REDACTED]
• [REDACTED]	CCI [REDACTED]	[REDACTED]	[REDACTED]
• [REDACTED]	CCI [REDACTED]	[REDACTED]	[REDACTED]
• Section 9.2 (Analysis Sets);	Revisions made on PK concentration set and PK parameter set.	Updates based on newly added objective and endpoint.	Substantial

Section # and Name	Description of Change	Brief Rationale	Substantial or Nonsubstantial
• Section 9.3.1 (Pharmacokinetic Analyses);	Added statement about salivary PK parameters.		
• [REDACTED]	CCI [REDACTED]	[REDACTED]	[REDACTED]
[REDACTED]	[REDACTED]	[REDACTED]	[REDACTED]
[REDACTED]	[REDACTED]	[REDACTED]	[REDACTED]
[REDACTED]	[REDACTED]	[REDACTED]	[REDACTED]
[REDACTED]	[REDACTED]	[REDACTED]	[REDACTED]

## 1. PROTOCOL SUMMARY

### 1.1. Synopsis

**Protocol Title:** A Phase 1, Open-Label, Randomized, Single Dose, Crossover Study to Estimate the Relative Bioavailability of Nirmatrelvir and Ritonavir Following Oral Administration of 4 Different Fixed Dose Combination Tablet Formulations Relative to The Commercial Tablet Formulation in Healthy Adult Participants Under Fasted Conditions

**Brief Title:** A Phase 1 Relative Bioavailability Study of Nirmatrelvir/Ritonavir 4 Different Fixed Dose Combination Tablets Relative to the Commercial Tablets in Healthy Participants.

### Regulatory Agency Identification Number(s):

US IND Number:	153517
EudraCT Number:	NA
ClinicalTrials.gov ID:	NA
Pediatric Investigational Plan Number:	NA
Protocol Number:	C4671023
Phase:	1

### Rationale:

Nirmatrelvir is a potent and selective inhibitor of the SARS-CoV-2 Mpro that is currently being developed as an oral treatment of COVID-19. Ritonavir is a strong CYP3A4 inhibitor being used to inhibit the metabolism of nirmatrelvir in order to increase plasma concentrations of nirmatrelvir to values that are efficacious. The clinical development program for nirmatrelvir includes 12 completed clinical studies: 8 Phase 1 studies in healthy participants (C4671001, C4671008, C4671012, C4671013, C4671014, C4671015, C4671019 and C4671024), 1 Phase 1 study in renal impairment participants (C4671011), 1 Phase 1 study in hepatic impairment participants (C4671010) and 2 Phase 2/3 pivotal studies in COVID-19 patients (C4671005 and C4671006).

The 4 different test formulations are designed to evaluate the effect of nirmatrelvir drug loading and disintegrant level on the performance of FDC tablets relative to the commercial product. The purpose of this study is to estimate the rBA of nirmatrelvir/ritonavir of 4 different FDC tablet formulations relative to the commercial tablet formulation under fasted conditions in healthy adult participants.

CCI

## Objectives and Endpoints:

Objectives	Endpoints

Primary:
 

• To estimate the rBA of the nirmatrelvir/ritonavir 300/100 mg (2 × 150/50 mg) FDC tablets Test formulation 1 (low disintegrant) compared to the nirmatrelvir/ritonavir 300 (2 × 150)/100 mg commercial tablets under fasted conditions (reference).

• To estimate the rBA of the nirmatrelvir/ritonavir 300/100 mg (2 × 150/50 mg) FDC tablets Test formulation 2 (high disintegrant) compared to the nirmatrelvir/ritonavir 300 (2 × 150)/100 mg commercial tablets under fasted conditions (reference).

• To estimate the rBA of the nirmatrelvir/ritonavir 300/100 mg (2 × 150/50 mg) FDC tablets Test formulation 3 (high drug load) compared to the nirmatrelvir/ritonavir 300 (2 × 150)/100 mg commercial tablets under fasted conditions (reference).

• To estimate the rBA of the nirmatrelvir/ritonavir 300/100 mg (3 × 100/33.3 mg ) FDC tablets Test formulation 4 compared to the nirmatrelvir/ritonavir 300 (2 × 150)/100 mg commercial tablets under fasted conditions (reference).

	
Primary:
 

• The test/reference ratios for <math>AUC_{inf}</math> (if data permits), <math>AUC_{last}</math>, and <math>C_{max}</math> of nirmatrelvir and ritonavir.

Secondary:
 

• To evaluate the safety and tolerability of nirmatrelvir/ritonavir in healthy participants.

	
Secondary:
 

• Assessment of TEAEs, clinical laboratory abnormalities, vital signs, PEs, and 12-lead ECGs.

## Overall Design:

This is a Phase 1, open-label, single-dose, randomized, crossover study in healthy adult participants to estimate rBA of nirmatrelvir/ritonavir 300/100 mg of 4 different FDC Test formulations compared to the nirmatrelvir/ritonavir 300/100 mg commercial tablets (Reference formulation) under fasted conditions. The study will also assess the safety and tolerability of nirmatrelvir/ritonavir FDC and commercial tablet formulations in healthy adult participants. **CCI**

The study will consist of 5 treatments:

- Single oral dose of nirmatrelvir/ritonavir 300 (2 × 150)/100 mg commercial tablets (Treatment A)
- Single oral dose of nirmatrelvir/ritonavir 300/100 mg (2 × 150/50 mg) FDC tablets Test formulation 1 (Treatment B; nirmatrelvir/ritonavir 150/50 mg, low disintegrant),
- Single oral dose of nirmatrelvir/ritonavir 300/100 mg (2 × 150/50 mg) FDC tablets Test formulation 2 (Treatment C; nirmatrelvir/ritonavir 150/50 mg, high disintegrant)
- Single oral dose of nirmatrelvir/ritonavir 300/100 mg (2 × 150/50 mg) FDC tablets Test formulation 3 (Treatment D; nirmatrelvir/ritonavir 150/50 mg, high drug load).
- Single oral dose of nirmatrelvir/ritonavir 300/100 mg (3 × 100/33.3 mg) FDC tablets Test formulation 4 (Treatment E; nirmatrelvir/ritonavir 100/33.3 mg),

All treatments will be administered under fasted condition. Between each treatment, a minimum of 4 days washout is proposed to minimize any residual nirmatrelvir and ritonavir concentrations prior to start of the next treatment.

Approximately 15 healthy male and/or female participants will be enrolled and randomized to the study. Participants who discontinue from the study for non-safety reasons may be replaced at the sponsor's discretion in collaboration with the investigator.

Healthy participants will be screened to determine eligibility within 28 days prior to study treatment. Medical history and results of PEs, vital signs, 12-lead ECGs, and clinical laboratory evaluations will determine eligibility. Eligible participants will be admitted to the PCRU on Day -1 and will be confined in the PCRU until discharge on Day 4 of Period 4.

On Day 1 of each period, participants will receive a single oral dose of study intervention nirmatrelvir/ritonavir 300/100 mg as per the randomization schedule. Study treatments will be administered with approximately 240 mL of ambient temperature water under fasted conditions (overnight fast and no food until 4 hours after dosing). Serial PK samples will be collected up to 72 hours post dose. **CC1**

Participants will be discharged from the PCRU on Day 4 of Period 4, following completion of all assessments.

If a participant has any clinically significant, study-related abnormalities at the conclusion of a scheduled inpatient portion of the study, the Pfizer medical monitor (or designated representative) should be notified and the participant may be asked to remain in the PCRU until such abnormalities are deemed not clinically significant, or it is safe for outpatient follow-up.

A safety follow-up call will be made to participants approximately 28 to 35 days from administration of the final dose of study intervention.

### **Number of Participants:**

Approximately 15 healthy male and/or female participants will be enrolled and randomized to 1 of 5 possible treatment sequences to ensure at least 12 participants will complete the study.

Note: "Enrolled" means a participant's, or their legally authorized representative's, agreement to participate in a clinical study following completion of the informed consent process and randomization. A participant will be considered enrolled if the informed consent is not withdrawn prior to participating in any study activity. Potential participants who are screened for the purpose of determining eligibility for the study, but do not participate in the study, are not considered enrolled, unless otherwise specified by the protocol.

### **Study Population:**

Key inclusion and exclusion criteria are listed below:

#### **Inclusion Criteria**

Participants must meet the following key inclusion criteria to be eligible for enrollment into the study:

1. Male and female participants who are overtly healthy as determined by medical evaluation including medical history, PE, laboratory tests, vital signs and standard 12-lead ECGs.

#### **Exclusion Criteria**

Participants with any of the following characteristics/conditions will be excluded:

1. Positive test result for SARS-CoV-2 infection on Day -1.
2. Participants who have received a COVID-19 vaccine within 7 days before screening or admission, or who are to be vaccinated with a COVID-19 vaccine at any time during the study confinement period.

### **Study Arms and Duration**

The study will consist of 5 treatments. Each enrolled participant will participate in 4 study periods to receive 4 different treatments according to the sequence determined by randomization:

- Treatment A: Single oral dose of nirmatrelvir/ritonavir 300 (2 × 150)/100 mg commercial tablets under fasted conditions (Reference)
- Treatment B: Single oral dose of nirmatrelvir/ritonavir 300/100 mg (2 × 150/50 mg) FDC tablets Test formulation 1 (low disintegrant) under fasted conditions (Test 1)

- Treatment C: Single oral dose of nirmatrelvir/ritonavir 300/100 mg (2 × 150/50 mg) FDC tablets Test formulation 2 (high disintegrant) under fasted conditions (Test 2)
- Treatment D: Single oral dose of nirmatrelvir/ritonavir 300/100 mg (2 × 150/50 mg) FDC tablets Test formulation 3 (high drug loading) under fasted conditions (Test 3)
- Treatment E: Single oral dose of nirmatrelvir/ritonavir 300/100 mg (3 × 100/33.3 mg) FDC tablets Test formulation 4 under fasted conditions (Test 4)

Participants will be randomly assigned to 1 of 5 sequences as below:

Treatment Sequence	Period 1	Period 2	Period 3	Period 4
Sequence 1 (N =3)	Treatment A	Treatment B	Treatment C	Treatment D
Sequence 2 (N =3)	Treatment B	Treatment C	Treatment D	Treatment E
Sequence 3 (N =3)	Treatment C	Treatment D	Treatment E	Treatment A
Sequence 4 (N =3)	Treatment D	Treatment E	Treatment A	Treatment B
Sequence 5 (N =3)	Treatment E	Treatment A	Treatment B	Treatment C

Between each treatment, a minimum of 4 days washout is proposed to minimize any residual nirmatrelvir and ritonavir concentrations prior to start of the next treatment. Participants will be discharged on Day 4 of Period 4, following completion of all assessments.

The total planned duration of participation from the Screening visit to the last follow-up phone call, is approximately 12 weeks.

Study Intervention(s)						
Intervention Name	Nirmatrelvir	Ritonavir	Nirmatrelvir/ ritonavir	Nirmatrelvir/ ritonavir	Nirmatrelvir/ ritonavir	Nirmatrelvir/ ritonavir
Arm Name (group of participants receiving a specific treatment or no treatment)	nirmatrelvir/ ritonavir commercial tablets	nirmatrelvir/ ritonavir commercial tablets	nirmatrelvir/ ritonavir FDC tablets Test formulation 1	nirmatrelvir/ ritonavir FDC tablets Test formulation 2	nirmatrelvir/ ritonavir FDC tablets Test formulation 3	nirmatrelvir/ ritonavir FDC tablets Test formulation 4
Unit Dose Strength(s)	150 mg	100 mg	150/50 mg	150/50 mg	150/50 mg	100/33.3 mg
Route of Administration	Oral	Oral	Oral	Oral	Oral	Oral
Use	Reference	Reference	Test 1	Test 2	Test 3	Test 4
IMP or NIMP/AxMP	IMP	NIMP	IMP	IMP	IMP	IMP

Study Arm(s)					
Arm Title	Nirmatrelvir/ ritonavir commercial tablets	Nirmatrelvir/ ritonavir FDC tablets Test formulation 1	Nirmatrelvir/ ritonavir FDC tablets Test formulation 2	Nirmatrelvir/ ritonavir FDC tablets Test formulation 3	Nirmatrelvir/ ritonavir FDC tablets Test formulation 4
Arm Type	Reference	Experimental	Experimental	Experimental	Experimental
Arm Description	Single oral dose of nirmatrelvir/ ritonavir 300 (2 x 150)/100 mg commercial tablets under fasted conditions (Reference)	Single oral dose of nirmatrelvir/ ritonavir 300/100 mg (2 x 150/50 mg) FDC tablets Test formulation 1 (low disintegrant) under fasted conditions (Test 1)	Single oral dose of nirmatrelvir/ ritonavir 300/100 mg (2 x 150/50 mg) FDC tablets Test formulation 2 (high disintegrant) under fasted conditions (Test 2)	Single oral dose of nirmatrelvir/ ritonavir 300/100 mg (2 x 150/50 mg) FDC tablets Test formulation 3 (high drug loading) under fasted conditions (Test 3)	Single oral dose of nirmatrelvir/ ritonavir 300/100 mg (3 x 100/33.3 mg) FDC tablets Test formulation 4 under fasted conditions (Test 4)

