## Sample Size Determination

Total of 15 participants will be enrolled, so that each treatment sequence will have 3 participants. A sample size of 15 participants will be sufficient to provide a reliable estimate of rBA and intrasubject variability of nirmatrelvir and ritonavir. Participants who withdraw from the study or discontinue treatment, or whose PK samples are considered to be nonevaluable with respect to the primary PK objective may be replaced at the discretion of the investigator upon consultation with the sponsor.

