**Table 1. Randomized Treatment Sequences**

Treatment Sequence	Period 1	Period 2	Period 3	Period 4
Sequence 1 (N =3)	Treatment A	Treatment B	Treatment C	Treatment D
Sequence 2 (N =3)	Treatment B	Treatment C	Treatment D	Treatment E
Sequence 3 (N =3)	Treatment C	Treatment D	Treatment E	Treatment A
Sequence 4 (N =3)	Treatment D	Treatment E	Treatment A	Treatment B
Sequence 5 (N =3)	Treatment E	Treatment A	Treatment B	Treatment C

Healthy participants will be screened to determine eligibility within 28 days prior to study treatment. Medical history and results of PEs, vital signs, 12-lead ECGs, and clinical laboratory evaluations will determine eligibility. Eligible participants will be admitted to the PCRU on Day -1 and will be confined in the PCRU until discharge on Day 4 of Period 4.

On Day 1 of each period, participants will receive a single oral dose of study intervention nirmatrelvir/ritonavir 300/100 mg as per the randomization schedule. Study treatments will be administered with approximately 240 mL of ambient temperature water under fasted conditions (overnight fast of at least 10 hours and no food until 4 hours after dosing). Serial PK samples will be collected up to 72 hours post dose. CCI

**CCI** [REDACTED]. Participants will be discharged from the PCRU on Day 4 of Period 4, following completion of all assessments.

If a participant has any clinically significant, study related abnormalities at the conclusion of a scheduled inpatient portion of the study, the Pfizer medical monitor (or designated representative) should be notified and the participant may be asked to remain in the PCRU until such abnormalities are deemed not clinically significant, or it is safe for outpatient follow-up. A safety follow-up call will be made to participants approximately 28 to 35 days from administration of the final dose of study intervention.

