## 9.1. Statistical Hypotheses

There are no statistical hypotheses for this study.

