### 9.3.2. Statistical Methods for PK Data

For the primary objective, natural log transformed AUCinf (if data permits), AUClast and Cmax for nirmatrelvir and ritonavir will be analyzed using a mixed effect model with sequence, period and treatment as fixed effects and participant within sequence as a random effect. Estimates of the adjusted mean differences (Test-Reference) and corresponding 90% confidence intervals will be obtained from the model. The adjusted mean differences and 90% confidence intervals for the differences will be exponentiated to provide estimates of the ratio of adjusted geometric means (Test/Reference) and 90% confidence intervals for the ratios. Treatment A will be the Reference treatment while Treatments B, C, D and E will be the Test treatments.

PK parameters, including plasma AUCinf (if data permits), AUClast, Cmax, and CCI [REDACTED] (if data permits) of nirmatrelvir and ritonavir will be summarized descriptively by treatment. For AUCinf (if data permits), AUClast, and Cmax, a listing of the individual participant ratios (Test/Reference) will be provided. Box and whisker plots for AUCinf (if data permits), AUClast, and Cmax, will be plotted by treatment.

The plasma concentrations of nirmatrelvir and ritonavir will be listed and descriptively summarized by nominal PK sampling time and treatment. Individual participant, as well as mean and median profiles of the plasma concentration time data will be plotted by treatment using actual (for individual) and nominal (for mean and median) times respectively. Mean and median profiles will be presented on both linear and semi-log scales.

Additional specifications about the tables, listings, and figures will be outlined in the SAP.

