## **9.5. Sample Size Determination**

A sample size of 15 evaluable participants will provide 90% CIs for the difference between treatments of  $\pm 0.1175$  and  $\pm 0.0924$  on the natural log scale for  $AUC_{\text{inf}}$  and  $C_{\text{max}}$  for nirmatrelvir, respectively, with 80% coverage probability.

Parameter	Estimated Effect (100*Test/Reference)	90% CI	CI Width
AUC inf	85%	0.7558, 0.9560	0.2002
	90%	0.8002, 1.0122	0.2119
	95%	0.8447, 1.0684	0.2237
	100%	0.8892, 1.1246	0.2355
	105%	0.9336, 1.1809	0.2473
	110%	0.9781, 1.2371	0.2590
	115%	1.0225, 1.2933	0.2708
C max	85%	0.7750, 0.9323	0.1573
	90%	0.8206, 0.9871	0.1665
	95%	0.8662, 1.0420	0.1758
	100%	0.9117, 1.0968	0.1851
	105%	0.9573, 1.1516	0.1943
	110%	1.0029, 1.2065	0.2036
	115%	1.0485, 1.2613	0.2128

These estimates are based on the assumption that within-participant standard deviations are 0.1752 and 0.1378 for lnAUCinf and lnCmax, respectively, as obtained from clinical Studies C4671008 and C4671014 in healthy participants.

In addition, a sample size of 15 evaluable participants will provide 90% CIs for the difference between treatments of  $\pm 0.1625$  and  $\pm 0.2201$  on the natural log scale for AUCinf and Cmax for ritonavir, respectively, with 80% coverage probability.

Parameter	Estimated Effect (100*Test/Reference)	90% CI	CI Width
AUC inf	85%	0.7225, 1.0000	0.2775
	90%	0.7650, 1.0588	0.2938
	95%	0.8075, 1.1177	0.3102
	100%	0.8500, 1.1765	0.3265
	105%	0.8925, 1.2353	0.3428
	110%	0.9350, 1.2941	0.3591
	115%	0.9775, 1.3530	0.3755
C max	85%	0.6821, 1.0592	0.3771
	90%	0.7222, 1.1215	0.3993
	95%	0.7623, 1.1838	0.4215
	100%	0.8025, 1.2461	0.4437
	105%	0.8426, 1.3085	0.4659
	110%	0.8827, 1.3708	0.4880
	115%	0.9228, 1.4331	0.5102

These estimates are based on the assumption that within-participant standard deviations are 0.2424 and 0.3282 for lnAUCinf and lnCmax, respectively, as obtained from clinical studies C4671008 and C4671014 in healthy participants that used nirmatrelvir/ritonavir commercial tablets.

Participants who withdraw from the study or discontinue treatment, or whose PK samples are considered to be nonevaluable with respect to the primary PK objective may be replaced at the discretion of the investigator upon consultation with the sponsor.

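### All four primary contrasts are against Treatment A, yet A is given no more often than each Test; splitting Sequence 2 so that A displaces three different Tests would narrow every primary CI by 3.6% to 6.7%

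*Protocol*

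**What the plan says.** There are five treatments and four periods (protocol synopsis, Study Arms and Duration): "Each enrolled participant will participate in 4 study periods to receive 4 different treatments according to the sequence determined by randomization". The sequences are listed there, under "Table 1. Randomized Treatment Sequences" in protocol 4.1, and in SAP 2.1. Sequence 2 is B-C-D-E. On allocation, the synopsis says: "Total of 15 participants will be enrolled, so that each treatment sequence will have 3 participants".

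Protocol 9.3.2 sets the comparisons: "Treatment A will be the Reference treatment while Treatments B, C, D and E will be the Test treatments". The output is described as: "Estimates of the adjusted mean differences (Test-Reference) and corresponding 90% confidence intervals will be obtained from the model". For the primary parameters, "a listing of the individual participant ratios (Test/Reference) will be provided". The example code in SAP Appendix 1 has four ESTIMATE statements, each against A. Protocol 9.1 adds: "There are no statistical hypotheses for this study".

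Protocol 9.5 gives 90% CI half-widths for 15 evaluable participants on the log scale: 0.1175 and 0.0924 for nirmatrelvir AUCinf and Cmax, and 0.1625 and 0.2201 for ritonavir, "respectively, with 80% coverage probability". The synopsis rationale and protocol 4.2 say that the four formulations were chosen to study drug loading and disintegrant level relative to the commercial product.

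**The concern.** Table 1 treats the five treatments alike, but the planned analysis does not. A enters all four primary contrasts, while each Test enters one. When one treatment is the common comparator, giving it more often usually improves all the comparisons against it.

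Under Table 1, each Test shares a participant with A in only 9 of 15 participants, which makes 36 direct Test/Reference pairs. The three Sequence 2 participants can have no individual Test/Reference ratio and inform the primary contrasts only indirectly. The primary objective is estimation without a hypothesis, so the width of the Test/Reference interval measures how well it is met. The question is whether the same participants and doses could give narrower intervals.

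**Working it through.** **Inputs.** Sequences: Table 1. Model: period and treatment fixed, participant within sequence random, sequence fixed (protocol 9.3.2, SAP Appendix 1). Within-participant SDs (protocol 9.5): nirmatrelvir 0.1752 (lnAUCinf) and 0.1378 (lnCmax); ritonavir 0.2424 and 0.3282. Confidence level 90%, coverage probability 80%.

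**Formula.** Half-width = t(0.95, df) × SD × √c × √(χ²(0.80, df)/df), where c is Var(Test−A) in units of the within-participant variance. Protocol 9.5 prints no formula; this one is inferred because it reproduces the stated figures.

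Residual df = 60 doses − 15 participants − 3 (period) − 4 (treatment) = 38. Then t = 1.6860, χ² = 45.08 and √(45.08/38) = 1.0891, so the multiplier is 1.6860 × 1.0891 = 1.8362.

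**Reproducing 9.5.** With c = 2/15: 1.8362 × 0.1752 × √(2/15) = 0.1175. The other SDs give 0.0924, 0.1625 and 0.2201. All four match. The factor 2/15 means that all 15 participants contribute both treatments of every contrast.

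**Table 1 as written.** Each treatment is given 12 times, three times in every period, and each pair of treatments occurs together in 9 participants. This is a balanced incomplete block design with block size 4, 5 treatments and pair count 9, so c = 2 × 4/(9 × 5) = 8/45 = 0.1778 for every contrast. For nirmatrelvir AUCinf, 1.8362 × 0.1752 × √0.1778 = 0.1356. The ratio to the stated width is √((8/45)/(2/15)) = √(4/3) = 1.155, about 15% wider.

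**Giving A to the Sequence 2 participants.** Sequences 1, 3, 4 and 5 are kept. The design matrix with 15 participant, 3 period and 4 treatment effects was inverted for each variant. A takes the period of the Test it displaces, and df stays at 38.

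| Replacement for the three B-C-D-E participants | c, Test−A | CI width against Table 1 |
|---|---|---|
| Three different Tests: A-C-D-E, B-A-D-E, B-C-A-E | 0.1652 (B, C, D); 0.1547 (E) | −3.6%; −6.7% |
| Same Test in all three: A-C-D-E × 3 | 0.2083 (B); 0.1565 (C, D, E) | **+8.3%**; −6.2% |
| Same Test in two: A-C-D-E × 2, B-A-D-E | 0.1819 (B); 0.1657 (C); 0.1553 (D, E) | **+1.1%**; −3.5%; −6.6% |

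The percentages are √(c/0.1778) − 1. For example, √(0.1652/0.1778) = 0.964 and √(0.2083/0.1778) = 1.083.

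**Half-widths.**

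| | Stated in 9.5 | Table 1 | Three different Tests (B, C, D / E) |
|---|---|---|---|
| Nirmatrelvir AUCinf | 0.1175 | 0.1356 | 0.1307 / 0.1265 |
| Nirmatrelvir Cmax | 0.0924 | 0.1067 | 0.1028 / 0.0995 |
| Ritonavir AUCinf | 0.1625 | 0.1877 | 0.1809 / 0.1751 |
| Ritonavir Cmax | 0.2201 | 0.2541 | 0.2449 / 0.2370 |

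The mean c is (3 × 0.1652 + 0.1547)/4 = 0.1625, against 0.1778. That is worth 15 × 0.1778/0.1625 = 16.4 participants, or about 1.4 extra. Direct pairs rise from 36 to 11 + 11 + 11 + 12 = 45.

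**What is given up.** Doses become A 15, E 12, and B, C and D 11 each. A falls in Periods 1 to 4 for 4, 4, 4 and 3 participants. Test-versus-Test c rises from 0.1778 to 0.2013 (B-C, B-D, C-D; CIs 6.4% wider) and to 0.1891 (pairs with E; 3.1% wider).

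**Robustness.** The mixed model with sequence fixed gives the same c values. Without the sequence term, at assumed between/within variance ratios of 0.5 and 2, Table 1 gives 0.1739 and 0.1765, and the three-different-Tests layout gives 0.1628/0.1531 and 0.1643/0.1542. The direction is unchanged.

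**The case against.** The best defence is that Table 1 is a sound design. It is connected, every treatment appears three times in every period, and all four primary contrasts have equal precision. The alternative breaks that symmetry and favours one Test. The formulations were chosen to study disintegrant level and drug load, which invites comparing B with C, or D with the other 150/50 mg tablets. For B, C and D, those comparisons lose more (6.4%) than the contrasts against A gain (3.6%).

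The gain also changes little. At a true ratio of 1, the nirmatrelvir AUCinf interval for B, C or D moves from about 0.873–1.145 to 0.877–1.140, and SAP 4.2 sets no decision rule. Safety is a secondary objective, and further objectives are redacted, so a reader who takes CI width as the study's only yield goes beyond the documents. Blood/plasma ratio samples are taken for A and B only, and the layout shown cuts B from 12 to 11 participants while raising A from 12 to 15.

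Most of this stands and limits the weight of the point. It does not remove it. The stated purpose is performance relative to the commercial product, and the visible plan has no Test-versus-Test contrast, ratio or objective. The documents give no reason for replicating the Reference no more than each Test.

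**Conclusion.** The point holds as an optional improvement worth considering. Every planned primary CI would be 3.6% (three Tests) or 6.7% (one Test) narrower with the same participants, doses and df, provided that the three Sequence 2 participants give up three different Tests in place. This rests on the planned model, complete data from 15 participants, and a common within-participant variance. The percentage gains do not depend on the SDs in 9.5.

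A reader might infer three stronger things, none of which is supported:

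- That giving A to those three participants helps in any form. The simplest edit, one replacement sequence for all three, widens the displaced Test's primary CI by 8.3%.
- That Table 1 is an error. It estimates all four contrasts validly and equally.
- That the change delivers the precision stated in 9.5. It recovers part of the gap only. The stated widths need c = 2/15, which neither layout has, and that roughly 15% gap is larger than the gain available here.

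**What to change.** Consider keeping Sequences 1, 3, 4 and 5 at three participants each and replacing Sequence 2 by A-C-D-E, B-A-D-E and B-C-A-E, one participant each. Any three different Tests will do. The Test left undisplaced keeps 12 participants and has the 6.7% gain, so the sponsor can choose which one that is (for example B, given the blood/plasma sampling, with B-A-D-E, B-C-A-E and B-C-D-A). If equal replication is preferred, for instance to keep comparisons among the formulations precise, state that reason in protocol 4.2.

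A change needs a new randomization list and edits to the synopsis table, Table 1, SAP 2.1, and the wording on five sequences and three participants per sequence. The model and ESTIMATE statements stay as they are. No participant, dose, visit or sample is added. The cost is the lost balance and the wider Test-versus-Test CIs shown above.

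Whichever layout is used, recompute the half-widths and interval tables in 9.5 with that layout's variance factor: 8/45 for Table 1, or 0.1652 and 0.1547 for the layout with three different Tests.
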